9.3 Dispensing Study Medication

Study medications will be provided at no cost to the participants. BUP-XR will be administered by study staff with appropriate licensure and training at induction and approximately every week during pregnancy. During the postpartum phase, women who are breastfeeding will continue

receiving BUP-XR weekly while women who are not breastfeeding may receive BUP-XR every four weeks; a possible exception is continued weekly BUP-XR for women who are not breastfeeding but for whom the prescribing clinician determines that 8 mg is the appropriate dose. Participants transitioning to monthly BUP-XR will be given the dose equating to their BUP-XR weekly dose (see **Table 7**). CAM2038 should be injected slowly into the subcutaneous tissue of the upper arm, abdomen, buttock or thigh. CAM2038 should not be administered in the same location for a minimum of 8 weeks for the weekly injection. No injection site rotation is needed for the monthly injection. BUP-XR must be dispensed/administered by a licensed medical practitioner appropriately trained and authorized to dispense study medications per local regulations. Dispensing frequency for BUP-SL (BUP/NX-SL) is at the clinician's discretion.

Participants who are discontinued, who do not wish to continue, or for whom community resources to continue are not available, the study may dispense sufficient BUP-SL for up to a two-week taper beginning at any time during treatment. All study medications shall be prepared and dispensed by a pharmacist or licensed medical practitioner appropriately trained and authorized to dispense study medications per local regulations.

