3.4 Treatments

Participants randomized to BUP-XR will receive a weekly formulation of CAM2038 during pregnancy. During the 12-month postpartum phase, women who are breastfeeding will continue

receiving BUP-XR weekly while women who are not breastfeeding will receive monthly BUP-XR. Participants randomized to BUP-SL will receive buprenorphine, with or without naloxone, based on site preference, during pregnancy and the 12-month postpartum phase.

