4.2 Rationale for Study Medications

4.2.1 CAM2038 vs. Sublocade™

Two BUP-XR products have been developed recently (CAM2038 from Braeburn Pharmaceuticals and Sublocade™ from Indivior), both of which are subcutaneously injected and form a gel deposit under the skin that releases BUP at a steady rate for up to one month; the CAM2038 product is also available as a weekly formulation. Sublocade™ received FDA approval in 2017. In 2018, the FDA determined that CAM2038 met all safety and efficacy standards necessary for approval but did not approve it for marketing due to exclusivity issues. The monthly formulations of both Sublocade™ and CAM2038 use N-methyl-2-pyrrolidone (NMP), a compound which animal studies suggest may have adverse fetal-infant effects, as an excipient.

The weekly CAM2038 product does not include NMP and, thus, was selected as the BUP-XR medication for MOMs. Specifically, the weekly CAM2038 product will be utilized while participants are pregnant or breastfeeding and the monthly formulation will be utilized during the postpartum phase for women who are not breastfeeding. The weekly CAM2038 product includes three excipients: 1) phosphatidylcholine; 2) glycerol dioleate (GDO); and 3) ethanol. The target weekly CAM2038 dose is 24 mg, but a minority of participants may require the highest dose (32 mg). The maximum potential exposure to the excipients for any participant/fetus would be for a pregnant woman randomizing into MOMs at 6 weeks EGA, delivering at 40 weeks, and receiving the maximum potential CAM2038 dose (32 mg of buprenorphine in 0.64 mL) every week. The maximum potential exposure to these excipients for any participant/breastfeeding infant postpartum would be for a participant receiving the 32 mg CAM2038 dose every week.

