7.6.3 General Measures

Treatment Services Review: The addiction-related treatment services received by participants during the prior 28 days will be assessed with the use of the Treatment Services Review, Version 6¹⁶⁷ according to the schedule in **Table 3**. CTN-0080 will utilize the version of the instrument created for use in CTN.

The Family Psychosocial Screener: A number of psychosocial stressors can impact infant development, including maltreatment, parental mental health, and domestic violence.^{168, 169} The Family Psychosocial Screener includes components designed to evaluate parental depression, intimate partner violence, parental history of abuse, and a number of other risk factors for developmental problems.¹⁷⁰ During initial development, it was shown to identify significantly more mothers with low self-esteem, depression, and history of abuse as a child than simply reviewing medical records.¹⁷¹ The instrument is a self-administered questionnaire that typically takes ≤10 minutes to complete. It will be completed by the individual completing the ASQ-3 at 6 and 12 months.

Pregnancy Test: During the postpartum phase, a urine pregnancy test will be completed prior to medication administration for BUP-XR participants receiving the monthly formulation. Additionally, a urine pregnancy test will be completed if the participant self-reports a new pregnancy.

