17.6 Pregnancy and Pregnancy Outcomes

Pregnancy outcomes will be captured as part of regular study data collection using information abstracted from the medical records for the participant and her neonate (if any). Pregnancy initiated in the 12-month post-partum period will not be considered an AE or SAE, but will be captured on a Pregnancy form.

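### The BUP-XR formulation rules conflict for a woman who becomes pregnant again postpartum and is not breastfeeding, and no consequence of a positive pre-dose pregnancy test is stated

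*Combined protocol and SAP*

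**What the plan says.** Section 4.2.1 explains the choice of product. The monthly formulation contains the excipient NMP, for which animal data raise the possibility of harm to the fetus or infant. The weekly formulation does not, and was chosen for that reason. The section then states that "the weekly CAM2038 product will be utilized while participants are pregnant or breastfeeding", and in the same sentence gives the monthly formulation to postpartum women who are not breastfeeding.

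Section 3.4 provides weekly dosing in pregnancy. For the postpartum phase it says that "women who are not breastfeeding will receive monthly BUP-XR".

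Section 9.3 has the injection given "approximately every week during pregnancy". It then says of the postpartum phase that "women who are not breastfeeding may receive BUP-XR every four weeks", with a possible exception for non-breastfeeding women "for whom the prescribing clinician determines that 8 mg is the appropriate dose". The note to Table 3 names breastfeeding as the condition for the weekly formulation and mentions no other.

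On new pregnancies, section 7.6.3 says that "a urine pregnancy test will be completed prior to medication administration for BUP-XR participants receiving the monthly formulation", and adds a test whenever a participant reports a new pregnancy. Table 3 schedules the test monthly for women on the monthly formulation. Section 17.6 says: "Pregnancy initiated in the 12-month post-partum period will not be considered an AE or SAE". It sends the event to a Pregnancy form.

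**The concern.** NMP is the protocol's own reason for using the weekly product around pregnancy. The postpartum dosing clauses do not carry that reason forward to a second pregnancy, although the plan expects such pregnancies and tests for them.

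At stake is a safeguard against fetal exposure, applied at about 10 sites. Two prescribers could each point to protocol text and act differently for the same woman: one to the pregnancy half of the sentence in 4.2.1, the other to its second half or to 3.4. A monitor could not say which of them had deviated from the protocol. The test result arrives immediately before an injection, which is when staff need a written next step.

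**Working it through.** There is no figure to reproduce, because the point concerns the wording of a rule. The check has four steps.

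**Step 1. Which participants meet conflicting rules?** Cross new pregnancy with breastfeeding, for a BUP-XR participant in the postpartum phase:

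| | Breastfeeding | Not breastfeeding |
|---|---|---|
| Not pregnant | weekly under every clause | monthly assigned (3.4, 4.2.1) or allowed (9.3) |
| Pregnant again | weekly under every clause | **conflict** |

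One cell of four is affected.

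**Step 2. Apply each clause to that cell.**

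| Place | What the clause turns on | Result for this woman |
|---|---|---|
| 4.2.1, first half of the sentence | pregnant or breastfeeding | weekly |
| 4.2.1, second half | postpartum, not breastfeeding | monthly |
| 3.4, postpartum clause | not breastfeeding | monthly (*will*) |
| 9.3, postpartum clause | not breastfeeding | monthly permitted (*may*) |
| 9.3, exception | clinician judges 8 mg appropriate | weekly possible, on grounds of dose |
| Table 3 note | breastfeeding | does not address her |
| 7.6.3 and Table 3 test row | on monthly formulation | tested; no consequence stated |
| 17.6 | new pregnancy | recorded on a form; nothing on dosing |

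The conflict is already present inside the one sentence in 4.2.1. There is a second, smaller inconsistency: 3.4 instructs where 9.3 permits.

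**Step 3. Do the during-pregnancy clauses in 3.4 and 9.3 settle it?** Not clearly. Each is followed by a separate postpartum clause, and section 8.5 describes the active phase as the pregnancy through about 12 months postpartum. A new conception in those 12 months is in the postpartum phase by that description, where the breastfeeding split applies. The clauses are not expressly limited to the index pregnancy either, so both readings are open.

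**Step 4. Is the consequence of a positive test stated elsewhere?**

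- Section 8.5 (active treatment): no.
- Section 8.7.1 (medication discontinuation): general investigator discretion; a new pregnancy is not among the listed reasons.
- Section 9.3: no branch for a positive test.
- Sections 9.4 and 9.5 (missed doses, non-response): silent.
- Section 17.6: the form only. That form appears neither among the administrative forms in 7.7 nor in Table 3.

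The decision point recurs. If monthly dosing started in postpartum week 1 and ran at 4-week intervals to the last planned injection at about week 49, there would be (49 − 1)/4 + 1 = 13 dosing occasions, each preceded by a test. This is a ceiling per woman. It does not say how many women will test positive.

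**The case against.** The strongest reply is that a sensible reader can comply with everything. Section 9.3, where dosing is set out, is permissive, so withholding the monthly product from a pregnant woman breaches nothing there. The first half of the 4.2.1 sentence covers any participant who is pregnant. Apart from a test on self-report, the postpartum test is scheduled only for women on the monthly formulation and comes before the dose, so it plainly looks intended as a check on that product. Section 8.7.1 lets the investigator stop medication when clinically appropriate. The operations manual and the investigator's brochure are not available here and may say more.

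Much of this stands, and it rules out several stronger readings:

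- A reader might infer that the protocol sends pregnant women to the monthly product. It does not: no passage directs that for a woman known to be pregnant.
- A reader might infer that breastfeeding is the sole criterion. It is not, given the 8 mg exception and the weekly dosing stated for pregnancy.
- A reader might infer that 9.3 undoes a clean rule in 4.2.1. The rule in 4.2.1 is not clean, because it contains the same postpartum split.
- A reader might infer that the test serves no purpose. Its purpose is evident; the step after a positive result is what is missing.

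The reply does not remove the contradiction. The permissive word in 9.3 does not help with 3.4 or with the second half of the 4.2.1 sentence, both of which are worded as instructions. The 8 mg exception concerns dose: Table 7 lists no monthly equivalent of the 8 mg weekly injection. General discretion to stop medication does not say which formulation rule governs. If the operations manual does cover a positive test, the protocol passages still disagree with each other.

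**Conclusion.** The point holds as a contradiction confined to one group, BUP-XR participants who are pregnant again in the postpartum phase and not breastfeeding, together with an unstated consequence of a positive pre-dose test. It bears on fetal safety, because one of the two stated rules, followed literally, gives the exposure that section 4.2.1 sets out to avoid. That makes it more than a missing detail.

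Its size in women cannot be given. The documents state no rate of new pregnancy, no breastfeeding proportion and no expected number on monthly dosing, and any count would rest on assumptions for all three.

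A reader might also infer damage to the trial's main results. The documents do not support that. The primary outcome is measured between randomization and delivery, NOWS severity concerns the index infant, and power and error rates are untouched. An effect on the postpartum opioid outcome has not been shown. The conclusion rests on the protocol text alone; whether sites have further instruction in the operations manual cannot be checked.

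**What to change.** Reconcile sections 3.4, 4.2.1, 7.6.3, 9.3, Table 3 with its note, and 17.6, so that one rule, worded the same way throughout, covers a new pregnancy as well as breastfeeding. Settle whether the postpartum clause instructs (3.4) or permits (9.3). State in 9.3 what follows a positive test before a monthly injection, and refer to that statement from 7.6.3 and 17.6. Which formulation or action applies is for the sponsor's clinical team to decide; none is proposed here.

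Optionally, link the Pregnancy form to the injection records already kept, so that any exposure of a new pregnancy to the monthly product can be listed. The listing belongs within the BUP-XR arm, since only that arm receives the product. Adding the form to 7.7 and Table 3 would complete the trail.

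The cost is a text amendment with its usual IRB approval and a note to sites. The test is already scheduled and injections are already documented, so no new procedure or participant visit is needed.

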9.3.1 Induction

Following randomization, participants will be inducted onto their assigned pharmacotherapy. Guidelines for induction are provided in the study operations manual.

BUP-XR assignment: Research suggests that participants already being treated with BUP-SL can safely be given the corresponding dose of BUP-XR (see **Table 7**).¹⁷⁵ For participants not being treated with BUP-SL, sites will utilize the induction setting (e.g., outpatient, inpatient, or other in-person setting such as home visit or community clinical location) being used by the clinic for BUP-SL. It should be noted that precipitated opioid withdrawal following BUP-XR administration is not expected for several reasons. First, precipitated withdrawal was not observed in the CAM2038 Phase 2²⁹ or Phase 3¹⁰⁴ trials. In fact, in the Phase 2 trial participants were stabilized inpatient on 30 mg of morphine four times daily by mouth and then inducted onto 24 or 32 mg weekly CAM2038 15 hours after the last morphine dose (as long as the COWS was ≥ 8) without precipitated withdrawal. In addition, the authors of the Phase 2 trial reported: *“Owing to a protocol error that may have been somewhat serendipitous, some participants received their first CAM2038 injection with little to no evidence of withdrawal (COWS score < 8); none experienced precipitated withdrawal”*.²⁹ Second, the slower time to onset of C_{max} with the injection (24 hours) versus sublingual buprenorphine/naloxone (2.5 hours) theoretically should decrease the risk of precipitated withdrawal from BUP-XR compared to BUP-SL. Thus, site protocols used for induction on BUP-SL should mitigate risk of precipitated withdrawal from CAM2038. Third, sites will be instructed to only administer the injection when the participants are in opioid withdrawal if they are not already taking BUP-SL.

If precipitated withdrawal does occur after CAM2038 administration, no additional buprenorphine should be given since the levels of buprenorphine will be steadily increasing until they reach a maximum concentration at 24 hours post-administration. Symptomatic non-opioid treatments may be offered as needed to treat withdrawal signs and symptoms as clinically indicated at each site. For example, ondansetron may be administered for nausea and vomiting, acetaminophen for aches and pain, hydroxyzine for anxiety/restlessness, loperamide for loose stool/diarrhea and cyclobenzaprine for muscle cramping. Sites may determine which non-opioid as-needed medications they want to administer, and these medications will be captured as concomitant medications. Reassurance and monitoring should continue until the withdrawal dissipates. Each site should clinically determine whether the withdrawal is severe enough to warrant: 1) a longer visit to allow time for reassessment, fetal monitoring (to assure continued viability of fetus) and

reassurance that the withdrawal is dissipating; 2) hospital admission (e.g., if participant's withdrawal is not subsiding and the withdrawal requires more intensive monitoring and treatment) – for example the participant is unable to stop vomiting and needs IV hydration, fetus needs more intensive monitoring, etc.; and/or 3) an unscheduled visit the following day in order to assure that the withdrawal has dissipated and the participant is stable. Each site must develop its own detailed SOP for handling precipitated withdrawal after CAM2038 administration, with the understanding that more buprenorphine should NOT be given within the 24-hour period after the injection was given. Sites may determine on a case-by-case basis if they want to give more buprenorphine after the 24-hour period after consultation with the site medically responsible investigator.

BUP-SL assignment: The BUP-SL induction procedures typically used by the site will be utilized. As each site already has clinical experience inducing patients onto BUP-SL, we will allow each site to develop its own SOP for handling precipitated withdrawal from BUP-SL and to determine if they want to give more buprenorphine in these cases.

All cases of precipitated withdrawal in either study arm will be considered adverse events. All medications given will be captured as concomitant medications. In the event that precipitated withdrawal leads to fetal monitoring, any action taken specifically as a result of the fetal monitoring will be documented.

9.4 Missed Doses

Study participants may miss doses for a number of reasons including incarceration. A participant who discontinues her medication, for any reason, and then returns to the clinic may be continued/re-induced on the medication to which she was randomized as long as it is clinically appropriate in the judgment of the prescribing clinician.

9.5 Clinical non-response

Participants with a sub-optimal clinical response to their medication, as determined by the prescribing clinician, may be referred for alternative treatment (e.g., methadone maintenance). Such participants will be encouraged to continue participating in the data collection aspects (e.g., research visits, urine collection, infant assessments) of CTN-0080.

9.6 Study Medication Management/Drug Accountability

Study sites are required to observe local, state, and federal regulations regarding receipt, custody, dispensing, and disposition of all study medications. Each site will maintain an adequate supply of unexpired study medications on site.

9.6.1 Storage

Study medication will be stored in compliance with federal, state, and local laws and institutional policy. Study medication will be stored in a secured location under the conditions specified by the investigator's brochure/package inserts and DEA requirements. Temperature logs should show a daily record of medication storage temperature.

9.6.2 Documentation

Upon receipt, the investigator, pharmacist, or authorized designee at each site is responsible for maintaining written inventory of the study medication obtained for the study. Appropriately qualified and trained study personnel maintain accurate and current accounting of all study medication by utilizing drug accountability records, which are made available for review by study monitors and other appropriate research personnel. Medication accountability records, including

perpetual inventory, will document the amount of study medication ordered, received, and medications administered to, dispensed to, and returned by an individual participant. As with all study documentation, medication accountability records must be maintained in accordance with Good Documentation Practices and must be attributable, legible, contemporaneous, original, accurate, and complete.

Accurate drug accountability records:

- Demonstrate that the study medication was dispensed according to the protocol;
- Document receipt of the study medication, date, lot #, expiration date, quantity, and dosage;
- Account for unopened, un-dispensed, unused, returned, waste, or broken medication;
- Dosing logs should record participant ID #, date dispensed, drug name, lot #, and amount dispensed;
- Indicate who dispensed or handled the study medication.

9.6.3 Used/Unused Medication

Study medication returned by a participant may not be re-issued for use. Unused study medication will be returned and logged into a perpetual inventory of study medication returned. Damaged, returned, expired, or unused study medication will be accounted for by the NIDA contract monitor and sent to the study central pharmacy which will arrange with a reverse distributor for eventual destruction. Other ancillary medications obtained for this study will be destroyed on site or sent for destruction per local institutional policies.

9.6.4 Lost Medication

At the discretion of the site study treatment team, very limited replacement of study medications will be permitted.

9.6.5 Medication Packaging

CAM2038 will be supplied in single use injection kits. The injection kit will be labeled for investigational use only.

Each individual package of sublingual medication, both the mono product and the buprenorphine/naloxone product, will contain the study drug information. The lot number, medication expiration date, and storage conditions, as well as manufacturer and distributor information, will be included on the medication. Each package will be labeled for investigational use only.

9.7 Concomitant Medications

Any medication (including prescription, over-the-counter, herbal supplements, and health store products) to be taken during the study ideally should be approved by the Medical Clinician. Participants who initiate treatment for OUD with methadone or extended-release naltrexone will need to be discontinued from study medication but can otherwise continue with study participation. Participants prescribed benzodiazepines or other CNS depressants should be cautioned to use them only as directed by their physician.

10.0 ANALYTICAL PLAN

10.1 Statistical Hypotheses for Primary Objective

10.1.1 Key Hypotheses

It is hypothesized that the BUP-XR, relative to the BUP-SL, group will: 1) not have greater illicit opioid use during pregnancy (primary, non-inferiority); 2) have lower infant NOWS severity (key secondary, superiority); and 3) not have greater postpartum illicit opioid use (key secondary, non-inferiority).

